### Assessment of Causality

The relationship between the occurrence of an AE and the IMP and the Comparator will be assessed using the categories presented below. For expedited reporting and all other purposes, the categories “none” and “unlikely” will represent no evidence or argument to suggest a causal relationship, while “possible”, “probable” and “definite” will be seen to convey that there is evidence or argument to suggest a causal relationship. Following worst case scenario all AEs without a causality assessment from the investigator will be classified as “possible”:

---

None	

• The time interval between the administration of the IMP or Comparator and the occurrence or worsening of the AE rules out a relationship, and/or

• another cause is established and there is no evidence of a (concomitant) causal connection with or worsening caused by the IMP or Comparator.

Unlikely	

• The time interval between administration of the IMP or Comparator and the occurrence or worsening of the AE makes a causal relationship unlikely, and/or

• the known effects of the IMP, Comparator or substance class provide no indication of a (concomitant) causal connection with or worsening caused by the IMP or Comparator and there is another cause which serves as an adequate explanation, and/or

• although the known effects of the IMP, Comparator or substance class make it possible to derive a plausible causal chain with regard to a (concomitant) causal connection or worsening; however, another cause is considerably more likely, and/or

• another cause of the AE has been identified and a (concomitant) causal connection with or worsening caused by the IMP or Comparator is unlikely.

Possible	

• A plausible causal chain with regard to a (concomitant) causal connection with / worsening of the AE can be derived from the pharmacological properties of the IMP, Comparator or substance class. However, other approximately equally likely causes are known, or

• although the pharmacological properties of the IMP, Comparator or substance class provide no indication of a (concomitant) causal connection with / worsening of the AE, there is no other known cause which provides an adequate explanation.

Probable	

• The pharmacological properties of the IMP, Comparator or substance class, and/or

• the course of the AE after discontinuation of the trial drug and possible subsequent re-exposure, and/or

• specific findings (e.g. positive allergy test or antibodies against the IMP / Comparator / metabolites) suggest a (concomitant) causal connection with / worsening of the AE resulting from the IMP or Comparator; however another cause cannot completely be ruled out.

Definite	

• The pharmacological properties of the IMP, Comparator or substance class and/or

• the course of the AE after discontinuation of the IMP or Comparator and possible subsequent re-exposure, and/or

• specific findings (e.g. positive allergy test or antibodies against the trial drug / metabolites) definitely indicate that there is a (concomitant) causal connection with / worsening of the AE resulting from the IMP or Comparator and there are no indications of other causes.

---

## 8.2.6 Solicited Adverse Events

After each vaccination subjects receive a memory aid to record solicited local and general AEs most likely to occur on the day of vaccination and the following 14 days (days 0-14; 15 day period).

All solicited symptoms observed after vaccination with details concerning the intensity and the course of the reaction should be documented there. The investigator or designee will collect this information during the following scheduled visits and transfer it to the CRF. Local and general reactions still ongoing after 14 days post vaccination will be measured or examined each day until resolution or Visit 10 (Group 1) or Visit 4 (Group 2) respectively.

In case of severe and unexpected local and/or general reactions, the subject should be instructed to contact the trial physician outside of scheduled trial visits.

### 8.2.6.1 Solicited Local Adverse Events

The solicited local symptoms pain, redness (erythema), swelling, induration, itching (pruritus) and vaccination site appearance (normal/healed, red spot, bump, reddish blister, whitish blister, scab, ulcer/crater, warmth, swollen >3in, red streaks, drainage) are to be documented in the memory aid by the subject.

To standardize procedures, uniform rulers will be handed out to all subjects for measurements of erythema, swelling and induration diameters, as will digital thermometers for oral measurements of body temperature.

#### Assessment of Intensity

Injection site erythema	size measured in diameter
Injection site swelling	size measured in diameter
Injection site induration	size measured in diameter

The maximum severity will be scored as follows:

0	=	0
1	=	< 30 mm
2	=	≥ 30 – <100 mm
3	=	≥ 100 mm

Injection site pruritus:

0	=	No symptoms
1	=	Mild: routine daily activities not impaired
2	=	Moderate: routine daily activities impaired
3	=	Severe: prevents routine daily activities

Injection site pain:

- 0 = No pain
- 1 = Pain when touched
- 2 = Pain when moving the limb
- 3 = Spontaneously painful

For red spot, bump, reddish blister, whitish blister, scabs, ulcers/craters, warmth, swollen > 3 in., red streaks or drainage the presence or absence of the symptom is captured in the memory aid. The injection site pruritus and injection site pain is rated by the subject in the memory aid.

Assessment of Causality

Solicited local AEs are defined as being related to the vaccine.

**8.2.6.2 Solicited General Adverse Events**

The solicited general symptoms body temperature, headache, myalgia, chills, nausea, fatigue, malaise, swollen lymph nodes, and are to be documented in the memory aid by the subject.

Assessment of Intensity

Subjects are asked to document the solicited general AEs in the memory aid as described in [Table 3](#) below. In the subject's memory aid, the grading of maximum symptom intensity is described in basic, easily understood language based on the following descriptions:

**Table 3 Grading of General Symptoms from the Subject's Memory Aid**

MedDRA coded Preferred Term General AEs	Grade	Maximum Severity
Body temperature*	0	< 99.5°F (< 37.5°C)
	1	≥ 99.5 – <100.4°F (≥ 37.5 – < 38.0°C)
	2	≥ 100.4 – <102.2 F (≥ 38.0 – < 39.0°C)
	3	≥ 102.2 – <104°F (≥ 39.0 – < 40.0°C)
	4	≥ 104°F (≥ 40.0°C)
Headache, Myalgia, Chills, Nausea, Fatigue, Malaise,	0	No symptoms
	1	Mild: routine daily activities not impaired
	2	Moderate: routine daily activities impaired
	3	Severe: prevents routine daily activities
Swollen lymph nodes	Yes/No	

\*Pyrexia is defined as oral temperature ≥ 100.4°F (≥ 38.0°C).

Assessment of Causality

Causal relationship between solicited general AEs and the vaccine will be assessed by the investigator using the same categories as for unsolicited AEs (see [Section 8.2.5](#)).

## 8.2.7 Cardiac Assessment

To evaluate the cardiac profile of MVA-BN®, targeted physical exams including auscultation of the heart and lung will be performed ([Section 8.2.3](#)). Any kind of cardiac signs (i.e. discovered by the physician during examination of the subject) or symptom(s) (i.e. experienced and reported by the subject) detected during the trial such as but not limited to chest pain, dyspnea, arrhythmia or edema are recorded.

### ECG

A standard 12-lead ECG will be taken at the Screening Visit, at Visit 3 for both groups, and at Visit 9 for Group 1 only. At Visit 6 (for Group 1 only) an ECG is only done if clinically indicated. ECGs will be evaluated by a centralized procedure. The workflow and communication flow will be provided in a separate manual.

### Cardiac Risk Factors

The individual cardiac risk factor is calculated before the first vaccination (for subjects 20 years of age and older), using the National Heart, Lung and Blood Institute's risk assessment tool (<http://cvdrisk.nhlbi.nih.gov/calculator.asp>). Subjects with a 10 percent or greater risk of developing a myocardial infarction or coronary death within the next 10 years are excluded from trial participation.

In addition, the family cardiac risk factor is evaluated at the Screening Visit. Subjects with an immediate family member (father, mother, brother, or sister), who has had onset of ischemic heart disease before 50 years of age are also excluded from trial participation.

### Troponin I

Troponin I will be measured at the Screening Visit and at Visit 3, and at Visit 9 for Group 1 only. At any other visits troponin I will only be measured if clinically indicated.

Cardiac events fulfill the definition of an AESI as described in [Section 8.3.2](#). The investigator will be asked to assess the clinical significance of the case.

Case definitions as published by the CDC ([MMWR, May 30, 2003](#)) are provided in [Appendix III; Section 17.3](#) in order to:

- help investigators to recognize possible events of acute myocarditis and/or pericarditis and
- distinguish from unspecific and isolated ECG abnormalities without or with unclear clinical significance.

### Questions:

The following specific cardiac questions will be routinely asked to the subject at the trial visits on the day of each vaccination; and the trial visits 2 weeks following each vaccination (Visits 3, 6

and 9 for Group 1; Visit 3 for Group 2) and 4 weeks following each vaccination (Visits 4, 7 and 10 for Group 1; Visit 4 for Group 2).

- Since your last visit, have you developed any chest pain, pressure, or discomfort that is beyond what is usual for you?
- Since your last visit, have you developed any shortness of breath at rest or exertion that is beyond what is usual for you?
- Since your last visit, have you noticed any swelling of your ankles, feet, or legs that is beyond what is usual for you?

If the answer to one of the question is "yes", further evaluations as outlined in [Figure 1](#) are initiated.

[figure not shown]
Subjects who develop any kind of cardiac signs or symptoms during the trial such as, but not limited to chest pain, dyspnea, arrhythmia or edema are referred to a local cardiologist for cardiac evaluation as described in the DoD Clinical Guidelines for Post-Smallpox Vaccine Associated Myopericarditis ([Appendix II; Section 17.2](#)). All treatment emergent AESIs will be followed up until complete resolution or until the sequelae are stable and considered to be permanent.

In any case of cardiac signs or symptoms, or increased laboratory results for Troponin I, the subject will be asked to attend for an unscheduled visit at the site, in order to perform or repeat Troponin I testing, to perform a physical examination for cardiac symptoms and to record an unscheduled ECG.

Further details regarding the follow-up of AESIs are described in the 'Investigator's Manual – Follow-up of Adverse Events of Special Interest'.

[Figure 1](#) outlines the algorithm for assessment of cardiac events.

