## 1.5 Trial Procedure Schedule

### Trial Procedure Schedule – Group 1

Visit (V)	SCR	V1	V2	V3	V4	V5	V6	V7	V8	V9	V10	Remote FU
Day / V +... d	-70- -1	0	V1 +6-8	V1 +13-15	V1 +27-29	V4 +6-8	V4 +13-15	V1 +55-57	V7 +6-8	V7 +13-15	V7 +27-29	Last Vaccination +182-210
Week	-10- -1	0	1	2	4	5	6	8	9	10	12	34-38
Procedures												
Informed consent	X											
Check inclusion / exclusion criteria	X	X										
Medical/Surgical History	X											
Check vaccination history and absence of vaccination scar	X											
Complete physical exam 	X											
Targeted physical exam 		X	(X)	X	X	(X)	X	X	(X)	X	X	(X)
Evaluation of vital signs	X	X	X	X	X	X	X	X	X	X	X	(X)
Recording of Baseline signs and symptoms	X	X										
Check cardiac risk factors	X											
ECG 	X			X			(X)			X		
Questions on cardiac signs and symptoms		X		X	X		X	X		X	X	
Review of prior/concomitant medications	X	X		X	X		X	X		X	X	(X)
Counseling 	X	X	X	X	X	X	X	X	X	X	X	
Examination of vaccination site		X	X	X	X	X	X	X	X	X	X	
Photo of vaccination site									X	X		
Bandage application / change 								X	X	X	X	
Assessment of axillary and supraclavicular lymphadenopathy		X	X	X	X	X	X	X	X	X	X	
SAE/AE/AESI recording		X	X	X	X	X	X	X	X	X	X	X 

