### Visit 2 (Visit 1 + 6-8 days)

The following tasks will be performed

- Targeted physical examination, including auscultation of heart and lungs (if clinically indicated); see [Section 8.2.3](#) for more details
- Evaluation of vital signs
- Counseling on avoidance of contact spread (specifically after ACAM2000® vaccination), HIV infection and pregnancy
- Assessment of axillary and supraclavicular lymphadenopathy; see [Section 8.2.3](#) for more details
- Examination of vaccination site
- Recording of AEs/SAEs/AESIs
- Review of memory aid
- Blood draw (serum collection) for antibody analysis (16 ml)

Group 2 only:

- Photo of vaccination site
- Bandage application/change

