### 5.1.3 Myocarditis and Pericarditis in the ACAM2000 Clinical Trial Experience

In clinical trials involving 2983 subjects who received ACAM2000 and 868 subjects who received Dryvax®, ten (10) cases of suspected myocarditis [0.2% (7 of 2983) ACAM2000 subjects and 0.3% (3 of 868) Dryvax® subjects] were identified. The mean time to onset of suspected myocarditis and/or pericarditis from vaccination was 11 days, with a range of 9 to 20 days. All subjects who experienced these cardiac events were naïve to vaccinia. Of the 10 subjects, 2 were hospitalized. None of the remaining 8 cases required hospitalization or treatment with medication. Of the 10 cases, 8 were sub-clinical and were detected only by ECG abnormalities with or without associated elevations of cardiac troponin I. All cases resolved by 9 months, with the exception of one female subject in the Dryvax® group, who had persistent borderline abnormal left ventricular ejection fraction on echocardiogram. The best estimate of risk for myocarditis and pericarditis is derived from the Phase 3 ACAM2000 clinical trials where there was active monitoring for potential of myocarditis and pericarditis. Among vaccinees naïve to vaccinia, 8 cases of suspected myocarditis and pericarditis were identified across both treatment groups, for a total incidence rate of 6.9 per 1000 vaccinees (8 of 1,162). The rate for the ACAM2000 treatment group were similar: 5.7 (95% CI: 1.9-13.3) per 1000 vaccinees (5 of 873 vaccinees) and for the Dryvax® group 10.4 (95% CI: 2.1-30.0) per 1000 vaccinees (3 of 289 vaccinees). No cases of myocarditis and/or pericarditis were identified in 1819 previously vaccinated subjects. The long-term outcome of myocarditis and pericarditis following ACAM2000 vaccination is currently unknown.

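### The scripted cardiac questions look back only to the previous visit but are skipped at the one-week visits, so the first 6 to 8 days after each dose fall outside every scripted recall window

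*Protocol*

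**What the plan says.** Protocol Section 8.2.7, under Questions, sets out three cardiac questions, on chest pain, shortness of breath and leg swelling. All three use the look-back seen in the first: "Since your last visit, have you developed any chest pain, pressure, or discomfort that is beyond what is usual for you".

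The timing is given in the same place. "The following specific cardiac questions will be routinely asked to the subject at the trial visits on the day of each vaccination", then at "the trial visits 2 weeks following each vaccination (Visits 3, 6" and 9 in Group 1, Visit 3 in Group 2), and then "4 weeks following each vaccination (Visits 4, 7 and 10 for Group 1; Visit 4 for Group 2").

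The schedule row "Questions on cardiac signs and symptoms" in Protocol Section 1.5 agrees. In Group 1 it is marked at Visits 1, 3, 4, 6, 7, 9 and 10 and blank at Visits 2, 5 and 8. In Group 2 it is marked at Visits 1, 3 and 4 and blank at Visit 2. SAP Tables 1 and 2 match. The task lists in Section 4.2.2 for Visits 2, 5 and 8 omit the questions, although each is a physical visit 6 to 8 days after a dose, as in "Visit 2 (Visit 1 + 6-8 days").

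Section 8.1.3.3 counts as an AESI any cardiac sign or symptom arising after the first vaccination. AESIs are a secondary safety endpoint (Section 9.3.2).

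**The concern.** The look-back and the visit schedule do not fit together. The visit before Visit 3 is Visit 2, before Visit 6 it is Visit 5, and before Visit 9 it is Visit 8. Take a subject with chest pain on day 3 that has settled by day 7 and is not volunteered at the one-week visit. That subject can truthfully answer no at day 14. The questions are then narrower than the AESI definition they serve, which runs from the first vaccination without a break.

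The other planned prompts for week 1 are thin. The memory aid (Section 8.1.3.2) does not solicit chest pain, breathlessness or leg swelling. Auscultation at the one-week visits is done only if clinically indicated. Section 8.2.7 gives evaluating the cardiac profile of MVA-BN as its purpose, so under-recording of early symptoms would affect a result that the trial means to describe.

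**Working it through.** The documents give no coverage figure to reproduce. The check assigns each between-visit interval to the visit that closes it, and counts the interval as covered only if the questions are asked at that visit.

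**Inputs.** The one-week visit is at dose + 6-8 days, the two-week visit at dose + 13-15 (taken as 14), and the four-week visit or next dose at about 28 (Section 1.5). On vaccination days the questions precede the dose (Section 4.2.2, Visits 1, 4 and 7), so they cover nothing after that dose.

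| Asked at | Previous visit | Days after the dose covered |
|---|---|---|
| Visit 3 (both groups) | Visit 2 | 6-8 to 14 |
| Visit 4 (both groups) | Visit 3 | 14 to 28 |
| Visit 6 (Group 1) | Visit 5 | 6-8 to 14 |
| Visit 7 (Group 1) | Visit 6 | 14 to 28 |
| Visit 9 (Group 1) | Visit 8 | 6-8 to 14 |
| Visit 10 (Group 1) | Visit 9 | 14 to 28 |

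**Uncovered after each dose:** day 0 to day 6-8.
- Share of 28 days: 6/28 = 21%, 7/28 = 25%, 8/28 = 29%.
- Share of the first 14 days at the nominal visit day: 7/14 = 50%.
- Group 1, three doses: 3 x 7 = 21 of 84 days, of which 2 x 7 = 14 of 56 follow MVA-BN.
- Group 2, one dose: 7 of 28 days.

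**Known onset times.** The ACAM2000 label in Appendix IVc (its Section 5.1.3) says the mean time to onset of suspected myo-/pericarditis "from vaccination was 11 days, with a range of 9 to 20 days". The latest uncovered day is 8, so that range lies wholly in the covered period. It comes from 10 cases, 7 after ACAM2000 and 3 after Dryvax. The documents give no onset range for MVA-BN.

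**Objective tests.** Routine ECG and troponin I fall at Screening, at Visit 3, and at Visit 9 in Group 1 (Section 8.2.7). After the second MVA-BN dose neither is routine: the Visit 6 ECG is conditional and the Visit 6 troponin cell is blank. The next routine tests are at Visit 9, nominally day 70, which is 70 - 28 = 42 days after that dose and 14 days after ACAM2000.

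**After the change.** If each set of questions reaches back to the previous set, the Group 1 windows are days 0-14, 14-28, 28-42, 42-56, 56-70 and 70-84. Uncovered time falls from 6-8 days per dose to 0.

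**The case against.** The strongest reply is that week 1 is watched by other means, and most of that reply stands.

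- The investigator asks about any adverse event since the previous visit at every active-phase visit (Section 8.1.3.1). AESIs are assessed at all trial visits (Section 8.2.5), and their recording is a listed task at Visits 2, 5 and 8. Day-3 chest pain is therefore asked about at day 6-8, though by an open question.
- Section 4.2.5 requires a Group 1 check before the doses at Visits 4 and 7. It names chest pain and shortness of breath and looks back to the first vaccination, so it spans both early MVA-BN weeks. It is not a scripted question, and nothing like it follows Visit 7 or applies to Group 2.
- Comparisons on secondary endpoints are descriptive (Section 9.6), so no confirmatory conclusion depends on this.

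Three stronger readings are tempting, and the documents do not support them.

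1. A reader might infer that week 1 is blind for the AESI endpoint. It is not, for the reasons above, and an AESI counts however it was elicited.
2. A reader might infer that only a yes to a scripted question starts the cardiac work-up. Section 8.2.7 also sends any cardiac sign or symptom to evaluation, and the note to Figure 1 adds scheduled ECG or troponin abnormalities. The figure itself was not available in the copy reviewed.
3. A reader might infer that the gap favours MVA-BN, because the label's ACAM2000 onsets fall in the covered period. MVA-BN timing is not given, and early symptoms after ACAM2000 meet the same gap. Eight of the label's 10 cases were sub-clinical and found only by ECG, with or without raised troponin, so symptom questions would not have found them. The Section 4.2.5 check also gives Group 1 an extra look.

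What the reply does not remove is that the plan prescribes specific prompts as routine after every vaccination, and their wording leaves out one week each time.

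**Conclusion.** The mismatch is real, and its size is certain on the literal wording: 6 to 8 days after every dose, nominally 25% of the four-week period, lie outside every scripted window. That is a share of days, not of missed events; the documents give nothing from which to estimate missed events.

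The consequence is modest: an open enquiry replaces three specific prompts, so transient early symptoms are less likely to be captured after either vaccine. Objective back-up is weakest after the second MVA-BN dose. No direction of bias between the vaccines is established.

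This rests on staff and subjects taking the look-back at face value. If sites already read it as reaching back to the last time the questions were asked, the gap closes in practice, but the protocol does not say so.

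**What to change.** Either change is enough.

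- **Reword (simplest).** In Section 8.2.7 and the source worksheet, replace the look-back with 'since we last asked you these questions' ('since screening' at Visit 1). Alternatively, use 'since your last vaccination' at Visits 3, 6 and 9. The windows then join up from the first vaccination, in line with Section 8.1.3.3. The cost is a two-week rather than a one-week recall period at Visits 3, 6 and 9.
- **Add.** Keep the wording and ask the same questions at the existing Visits 2, 5 and 8 in Group 1 and Visit 2 in Group 2. This keeps recall short. It takes a few minutes at three Group 1 visits and one Group 2 visit, plus matching edits to Sections 1.5, 4.2.2 and 8.2.7 and SAP Tables 1 and 2.

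Neither needs a new visit, test or member of staff.

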**Figure 1: Algorithm for Assessment of Cardiac Events**

\*At any protocol-scheduled ECG and/or troponin I abnormality, the algorithm will begin at this point.

## 8.2.8 Safety Laboratory Measurements

The intensity of laboratory / systemic quantitatively measured toxicities will be graded according to the toxicity scale in [Appendix I; Section 17.1](#). These grading scales include the laboratory values determined with the routine safety parameters. In case of other laboratory values not included in the routine safety laboratory and not listed in [Appendix I; Section 17.1](#), the [National Cancer Institute Common Toxicity Criteria Table, Version 4.03, published June 14, 2010](#) will be used for grading of laboratory toxicities.

Safety laboratory (hematology and serum chemistry) is determined at the Screening Visit and Visit 3 for all subjects and at Visit 6 and Visit 9 for Group 1 only. If clinically indicated Safety laboratory tests can be performed at any other visit(s). The safety laboratory measurements are performed at the site specific local laboratory. Laboratory normal ranges are provided by the local laboratory and filed in the Regulatory File. Safety laboratory parameters to be evaluated are:

